7.4 Dose Modifications

Dose delays and modifications should be recorded in the patient's notes and entered onto the appropriate IcICLLe treatment form.

7.4.1 Ibrutinib

Recommendations for Ibrutinib dose modifications are provided in Table 4; variations from these recommendations may be warranted based on an investigator's individual judgment in considering potential risks, benefits, and therapeutic alternatives available to each subject.

The ibrutinib dose should be withheld for any unmanageable, potentially drug-related toxicity that is Grade 3 or higher in severity. Any other clinically important events where dose delays may be considered appropriate by the Investigator must be discussed with the clinical coordinator via the trials office.

Ibrutinib may be withheld for a maximum of 28 consecutive days for toxicity. Study treatment should be discontinued in the event of a toxicity lasting more than 28 days.

The dose of ibrutinib should be modified according to the dose modification guidelines in Table 4 if any of the following toxicities occur:

- Grade 4 neutropenia ($0.5 \times 10^9/L$) for more than 7 days. The use of neutrophil growth factors is permitted.
- Grade 3 thrombocytopenia ($50 \times 10^9/L$) for subjects with normal platelet count at baseline; or, for subjects with baseline thrombocytopenia, a platelet decrease of 50% to 74% from baseline in the presence of significant bleeding.
- Grade 4 thrombocytopenia ($25 \times 10^9/L$); or for subjects with baseline thrombocytopenia, a platelet decrease of $\geq 75\%$ from baseline or $< 20 \times 10^9/L$, whichever is higher.
- Grade 3 or 4 nausea, vomiting, or diarrhoea if persistent, despite optimal anti-emetic and/or anti-diarrheal therapy.
- Any other Grade 4 toxicity
- Any unmanageable Grade 3 toxicity

Table 4: Recommendations for ibrutinib dose modifications

Events	Occurrence	Action to be Taken
Grade 2 cardiac failure	First	Withhold until recovery to \leq Grade 1 or baseline; may restart at 280 mg daily
	Second	Withhold until recovery to \leq Grade 1 or baseline; may restart at 140 mg daily
	Third	Discontinue
Grade 3 cardiac arrhythmias	First	Withhold until recovery to \leq Grade 1 or baseline; may restart at 280 mg daily
	Second	Discontinue
Grade 3 or 4 cardiac failure Grade 4 cardiac arrhythmias	First	Discontinue
Grade 3 or 4 non-haematological toxicities Grade 3 or 4 neutropenia with infection or fever Grade 4 haematological toxicities	First	Withhold until recovery to \leq Grade 1 or baseline; may restart at original dose level
	Second	Withhold until recovery to \leq Grade 1 or baseline; may restart at 1 dose level lower (280 mg per day)
	Third	Withhold until recovery to \leq Grade 1 or baseline; may restart at 1 dose level lower (140 mg per day)
	Fourth	Discontinue

At the Investigator's discretion, the dose of ibrutinib may be re-escalated after 2 cycles of a dose reduction in the absence of a recurrence of the toxicity that led to the reduction.

Dose Modification for Hepatic Impaired Subjects

Ibrutinib is metabolized in the liver and therefore subjects with clinically significant hepatic impairment at the time of screening (Child- Pugh class B or C) are excluded from study participation.. Concomitant use of strong CYP inhibitors is not permitted in subjects with chronic hepatic impairment. For subjects with existing chronic mild hepatic impairment (Child-Pugh class A) at enrolment, the starting dose has to be adjusted to a level of 280 mg daily (two capsules). For subjects who develop mild liver impairment while on study (Child-Pugh class A), the recommended dose reduction for ibrutinib is to a level of 280 mg daily (two capsules). For subjects who develop moderate liver impairment while on study (Child-Pugh class B), the recommended dose reduction is to a level of 140 mg daily (one capsule). Subjects who develop severe hepatic impairment (Child-Pugh class C) must hold study drug until resolved to moderate impairment (Child-Pugh class B) or better. Subjects who develop acute hepatic toxicity with liver enzymes Grade 3 or higher while on study should be managed per standard dose modification guidelines in Section 7.4.

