7.1.1 Ibrutinib treatment

Ibrutinib 420mg (3 x 140-mg capsules) should be taken orally once daily with the first dose taken on day 0 of treatment. The capsules are to be taken around the same time each day with 8 ounces (approximately 240 mL) of water. The capsules should be swallowed intact and patients should not attempt to open capsules or dissolve them in water. The use of strong CYP3A inhibitors/inducers, and grapefruit and Seville oranges should be avoided for the duration of the trial (Appendix 10). The use of Angiotensin-Converting Enzyme (ACE) inhibitors and Angiotensin Receptor Blockers (ARBs) are prohibited for patients receiving ibrutinib (Appendix 10).

- Patients who have a delay in administration of a dose of the study drug of <6 hours should take the planned dose as soon as possible after the intended time of administration. If the delay in administration of study drug is ≥6 hours, the dose should be skipped. Study drug administration may continue the next day at the usual time but the missed dose should not be made up.
- Vomited Ibrutinib doses may be retaken, but only if the capsule is visible in the vomit.
- If a patient experiences an ibrutinib overdose, consideration should be given as to whether ibrutinib administration should be temporarily interrupted. If the overdose ingestion is recent and substantial, use of gastric lavage or induction of emesis may be considered. Observation for any symptomatic side effects should be instituted, and biochemical and haematological parameters should be followed closely. Appropriate supportive management to mitigate adverse effects should be initiated.

Dose modifications and delays for ibrutinib are detailed in Section 7.4.1. Precautions for use are detailed in Section 7.8.

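### For a patient already on 280 mg ibrutinib, the second Grade 3-4 row of Table 4 contradicts itself: one level lower is 140 mg, but the bracket prints 280 mg

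*Protocol*

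**What the plan says.** The standard dose is set in Protocol 7.1.1: "Ibrutinib 420mg (3 x 140-mg capsules) should be taken orally once daily". The same section adds "The capsules should be swallowed intact and patients should not attempt to open capsules", so the usable daily levels are 420, 280 and 140 mg.

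Section 7.4.1 then directs that, for listed toxicities, "The dose of ibrutinib should be modified according to the dose modification guidelines in Table 4". It also says that "variations from these recommendations may be warranted" on the investigator's judgement. Within Table 4:

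- First Grade 2 cardiac failure and first Grade 3 arrhythmia: "may restart at 280 mg daily".
- Second Grade 2 cardiac failure: restart at 140 mg.
- General Grade 3-4 group, first occurrence: back to the original dose. Second: "may restart at 1 dose level lower (280 mg per day". Third: "may restart at 1 dose level lower (140 mg per day". Fourth: discontinue.

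The hepatic paragraph below the table says that for patients with mild chronic impairment (Child-Pugh A) at enrolment "the starting dose has to be adjusted to a level of 280 mg daily (two capsules". It recommends the same 280 mg for patients who develop Child-Pugh A impairment on study. It gives no separate ladder for these patients, and it sends acute liver-enzyme toxicity of Grade 3 or higher back to the standard guidelines of section 7.4. Section 7.7.2 sets 280 mg while a moderate CYP3A inhibitor is in use.

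**The concern.** The milligram figures in Table 4 are fixed numbers that fit a 420 mg start, yet other text puts some patients on 280 mg. In the second Grade 3-4 row the instruction is relative (go down one level) and the figure is absolute (280 mg). The two agree only if the patient is taking 420 mg.

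What is at stake is dosing after a repeat severe toxicity. A site that follows the figure gives a 280 mg patient the same dose that preceded the event. A site that follows the words gives half of it. Patients with Child-Pugh A impairment, started lower on purpose because the liver metabolises the drug, are among those affected.

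**Working it through.** **Inputs.** The capsule size of 140 mg and standard dose of 420 mg come from 7.1.1. The restart doses come from Table 4 in 7.4.1. The 280 mg routes come from the hepatic paragraph of 7.4.1, from 7.7.2, and from Table 4 itself where a patient was reduced earlier for another type of event. That last route assumes that occurrences are counted separately within each event group, which the table does not spell out.

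**Row count.** Table 4 has 10 rows: 5 print a reduced dose in mg, 1 returns to the original dose and 4 say discontinue (5 + 1 + 4 = 10).

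**The plan's own figures, from 420 mg.** One level lower is 420 - 140 = 280 mg at the second Grade 3-4 occurrence, and 280 - 140 = 140 mg at the third. Both printed figures are reproduced, so the table is consistent for the standard dose.

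**The same rows for a patient taking 280 mg.** Change = printed dose - current dose.

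| Row | Printed | Change from 420 mg | Change from 280 mg |
|---|---|---|---|
| Grade 2 cardiac failure, first | 280 | -140 (33% cut) | 0 |
| Grade 2 cardiac failure, second | 140 | -280 (67% cut) | -140 (50% cut) |
| Grade 3 arrhythmia, first | 280 | -140 (33% cut) | 0 |
| General Grade 3-4, second | 280 | -140 (33% cut) | 0 |
| General Grade 3-4, third | 140 | -280 (67% cut) | -140 (50% cut) |

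From 420 mg, 5 of 5 figures are reductions. From 280 mg, 2 of 5 are reductions and 3 of 5 leave the dose unchanged. Of those three, only the second general Grade 3-4 row also states that the dose goes down.

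**Dose path in the general Grade 3-4 group (restart dose after events 1, 2, 3, 4).**

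- Start 420 mg, by figure or by words: 420, 280, 140, stop. The first cut is at event 2.
- Start 280 mg, by figure: 280, 280, 140, stop. The first cut is at event 3.
- Start 280 mg, by words: 280, 140, then 140 - 140 = 0. There is no level below one intact capsule, so the third row's relative instruction names no dose.

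For a 280 mg patient the two readings differ by 280 - 140 = 140 mg at event 2, and following the words leaves the step at event 3 undefined.

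**The case against.** The best reply is that the words govern: the relative instruction is the rule, the bracket is its result from 420 mg, and a clinician holding drug for a second severe toxicity is unlikely to read 280 mg as a reduction from 280 mg. Table 4 is headed as recommendations, every restart is optional, and 7.11.1 lists unacceptable toxicity as a reason to stop treatment. The affected group is also narrow. Section 4.2 excludes Child-Pugh B and C, section 4.1 limits liver enzymes and bilirubin at entry, and the conflict needs a patient on 280 mg, a second qualifying event and a restart.

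Most of this stands as a limit on the harm. It does not settle the text. Freedom to depart from a recommendation does not say which of two doses is recommended, and following the words leads to 140 mg with no defined next step.

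Two stronger readings are tempting. A reader might infer that all three 280 mg rows are errors for these patients. The two cardiac rows name an absolute dose and do not claim that it is lower. They give a 280 mg patient no cut, but nothing in the protocol shows that a further cut was intended, so that is a clinical choice for the sponsor to confirm. A reader might also infer that 7.7.2 leaves a patient already on 280 mg without an option when a moderate CYP3A inhibitor is unavoidable. Section 7.7 refers the reader to Appendix 10, which already allows withholding, so that option is not missing.

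**Conclusion.** The contradiction is real and confined to one row: for a patient taking 280 mg, the second-occurrence Grade 3-4 row gives 140 mg by its words and 280 mg by its figure. By the printed figures, the first reduction for such a patient comes at event 3, compared with event 2 for a patient on 420 mg.

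This rests on the protocol's own capsule size and on at least one of its routes to 280 mg. The Child-Pugh A starting dose suffices, and it does not depend on how occurrences are counted. The protocol does not say how many patients take 280 mg, and the finding does not need that number. Few are likely to be affected.

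A reader might infer that the efficacy result is at risk. It is not: the primary estimate, the activity decision rule and the sample size are unaffected. This is a dosing-safety ambiguity that should be corrected because the correction is small.

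**What to change.** Add a note under Table 4 with three statements:

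1. The bracketed mg figures in the Grade 3-4 rows apply to patients taking 420 mg at the first occurrence.
2. A patient taking 280 mg restarts at 140 mg after a second occurrence. The sponsor states the step after that, for example discontinuation.
3. No printed figure in any row permits a restart above the dose taken at the event. This covers patients already on 140 mg. It concerns the restart only and leaves the later re-escalation allowed by 7.4.1 as it is.

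The sponsor should also confirm whether the two first-occurrence cardiac rows intend a cut for a patient on 280 mg. The first Grade 3-4 row, which returns to the original dose, stays as it is, and 7.7.2 needs no change on this account.

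The cost is a short protocol amendment, with no change to data collection or analysis. Because this is a dosing instruction, the sponsor should expect it to be handled formally: the amendment log shows that the last change to the moderate-inhibitor dose was part of a substantial amendment (version 12.0). If discontinuation is chosen as the next step, a 280 mg patient would stop at the third event, one event earlier than the printed ladder's fourth.

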7.7.2 Concomitant Medications to be Used With Caution with ibrutinib

Agents that may increase ibrutinib plasma concentrations:

Ibrutinib is metabolized primarily by CYP3A. Avoid co-administration with strong CYP3A4 or moderate CYP3A inhibitors and consider alternative agents with less CYP3A inhibition.

If a strong CYP3A inhibitor (eg, ketoconazole, indinavir, nelfinavir, ritonavir, saquinavir, clarithromycin, telithromycin, itraconazole, nefazadone, or cobicistat) must be used, reduce ibrutinib dose to 140 mg for the duration of the inhibitor use or withhold treatment temporarily (for 7 days or less).. Subjects should be monitored for signs of ibrutinib toxicity.

If a moderate CYP3A inhibitor (eg, voriconazole, erythromycin, amprenavir, aprepitant, atazanavir, ciprofloxacin, crizotinib, darunavir/ritonavir, diltiazem, fluconazole, fosamprenavir, imatinib, verapamil, amiodarone, or dronedarone) must be used, reduce ibrutinib to 280 mg for the duration of the inhibitor use. Avoid grapefruit and Seville oranges during ibrutinib/placebo treatment, as these contain moderate inhibitors of CYP3A

No dose adjustment is required in combination with mild inhibitors.

Avoid concomitant use of strong CYP3A inducers (eg, carbamazepine, rifampin, phenytoin, and St. John's Wort). Consider alternative agents with less CYP3A induction.

A list of common CYP3A inhibitors and inducers is provided in Appendix 10. A comprehensive list of inhibitors, inducers, and substrates may be found at <http://medicine.iupui.edu/clinpharm/ddis/main-table/>. This website is continually revised and should be checked frequently for updates.

For the most comprehensive effect of CYP3A inhibitors or inducers on ibrutinib exposure, please refer to the current version of the IB.

Agents that may decrease ibrutinib plasma concentrations:

Administration of ibrutinib with inducers of CYP3A4 can decrease ibrutinib plasma concentrations.

Co-administration of ibrutinib with strong CYP3A inducers, rifampin, in healthy subjects decrease ibrutinib plasma concentrations by approximately 10-fold. Avoid concomitant use of strong CYP3A inducers (eg, carbamazepine, rifampin, phenytoin, and St. John's Wort). Consider alternative agents with less CYP3A induction.

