APPENDIX 10 – CAUTIONED AND PROHIBITED MEDICATION

Some inhibitors of CYP3A4/5 are defined below.

Some cautioned and prohibited medications are listed below. This list is not exhaustive, any new medications should be reviewed with guidance from pharmacy in order to identify potential interactions.

Class of drug	Examples	During trial
Strong inhibitors of CYP3A	Boceprevir, clarithromycin, cobicistat, conivaptan, itraconazole, ketoconazole, nefazodone, nelfinavir, posaconazole, ritonavir (alone or in combination with one or more of the following: danoprevir, elvitegravir, indinavir, lopinavir, ombitasvir, paritaprevir, saquinavir, tipranavir), telaprevir, telithromycin, troleandomycin, voriconazole. Grapefruit juice, Seville oranges, starfruit.	Avoid the use of these drugs If a strong CYP3A inhibitor must be used, reduce ibrutinib dose to 140 mg or withhold treatment for the duration of inhibitor use withhold treatment temporarily (for 7 days or less). Patients should be monitored for signs of ibrutinib toxicity. If the patient must receive these drugs the patient must be monitored for toxicity.
Moderate inhibitors of CYP3A	Aprepitant, cimetidine, ciprofloxacin, clotrimazole, crizotinib, cyclosporine, dronedarone, erythromycin, fluconazole, fluvoxamine, imatinib, tofisopam, verapamil.	Avoid the use of these drugs If a moderate CYP3A inhibitor must be used, reduce ibrutinib dose to 280 mg or withhold treatment for the duration of inhibitor use. Patients should be monitored for signs of ibrutinib toxicity. If the patient must receive these drugs the patient must be monitored for toxicity.
Weak inhibitors of CYP3A	Chlorzoxazone, cilostazol, fosaprepitant, istradefylline, ivacaftor, lomitapide, ranitidine, ranolazine, tacrolimus, ticagrelor.	These drugs may be administered and patients should be monitored for any toxicity/lack of efficacy.
Strong inducers of CYP3A	Carbamazepine, enzalutamide, mitotane, phenytoin, rifampicin, St. John's wort.	Avoid the use of these drugs. Where use cannot be avoided this should be discussed with the Chief Investigator/Clinical Coordinator via the Trial Office. If the patient must receive these drugs the patient must be monitored for lack of efficacy.

Class of drug	Examples	During trial

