Moderate inducers of CYP3A	Bosentan, efavirenz, etravirine, modafinil.	
Avoid the use of these drugs.
 
Where use cannot be avoided this should be discussed with the Chief Investigator/Clinical Coordinator via the Trial Office.
 
If the patient must receive these drugs the patient must be monitored for lack of efficacy.

Weak inducers of CYP3A	Armodafinil, rufinamide.	
These drugs may be administered and patients should be monitored for any lack of efficacy.

CYP3A4 substrates sensitive to gut CYP3A metabolism	Dihydroergotamine, ergotamine, fentanyl, cyclosporine, sirolimus and tacrolimus	
Based on in vitro data, ibrutinib is a weak reversible inhibitor towards CYP3A4 at the intestinal level and may therefore increase the exposure to CYP3A4 substrates sensitive to gut CYP3A metabolism. No clinical data are available on this interaction. Caution should be exercised if co-administering ibrutinib with CYP3A4 substrates administered orally with narrow therapeutic range

ACE inhibitors	Ramipril, Lisinopril, Perindopril, Enalapril, Fosinopril, Imidapril, Quinapril, Trandolapril, Captopril	
ACE inhibitors are prohibited for patients receiving ibrutinib.
 
Participants should be moved to an alternative antihypertensive treatment. Where use cannot be avoided, ibrutinib should be stopped and discussed with the Chief Investigator/Clinical Coordinator and the Trial Office.

ARBs	Azilsartan, Candesartan, Eprosartan, Irbesartan, Losartan, Olmesartan, Telmisartan, Valsartan	
ARBs are inhibitors are prohibited for patients receiving ibrutinib.
 
Participants should be moved to an alternative antihypertensive treatment. Where use cannot be avoided ibrutinib should be stopped and discussed with the Chief Investigator/Clinical Coordinator and the Trial Office.

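### Voriconazole is a moderate CYP3A inhibitor in section 7.7.2 but a strong one in Appendix 10, so the protocol gives two different ibrutinib doses for the same patient

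*Protocol*

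**What the plan says.** Section 7.7.2 tells sites to avoid strong and moderate CYP3A inhibitors, then gives a last-resort dose for each class.

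- **Strong, section 7.7.2.** If one "must be used, reduce ibrutinib dose to 140 mg for the duration of the inhibitor use or withhold treatment temporarily (for 7 days or less" (the sentence closes there).
- **Moderate, section 7.7.2.** The examples begin "If a moderate CYP3A inhibitor (eg, voriconazole, erythromycin", and the instruction is that if one "must be used, reduce ibrutinib to 280 mg for the duration of the inhibitor use".
- **Strong, Appendix 10.** The examples in this row include "telithromycin, troleandomycin, voriconazole". The action, after advice to avoid these drugs, is "reduce ibrutinib dose to 140 mg or withhold treatment for the duration of inhibitor use withhold treatment temporarily (for 7 days or less".
- **Moderate, Appendix 10.** Voriconazole is not among the examples. The action is 280 mg, or a hold for as long as the inhibitor is given.

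Sections 7.7 and 7.7.2 both send the reader to Appendix 10 for the list of drugs.

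Section 7.4.1 adds a rule for patients with liver disease: "Concomitant use of strong CYP inhibitors is not permitted in subjects with chronic hepatic impairment". Such patients can be on trial. The next sentence says that for those with "existing chronic mild hepatic impairment (Child-Pugh class A) at enrolment, the starting dose has to be adjusted to a level of 280 mg daily". The strong-inhibitor text in section 7.7.2 and Appendix 10 does not mention hepatic impairment or refer back to section 7.4.1.

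**The concern.** Ibrutinib is an investigational product here, and these are the instructions a site follows when it has to give an interacting drug. Each text looks complete when read alone, so a site that has opened only one has no reason to suspect a conflict. One of the two doses must be unintended, and the protocol does not say which.

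The class also decides whether the hepatic bar in section 7.4.1 applies at all, because that bar covers strong inhibitors only. For a Child-Pugh A patient, the voriconazole mismatch is the difference between carrying on at the same dose and a combination that is not allowed.

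The need can arise during treatment. Section 7.8.12 reports fungal infections on ibrutinib, and section 7.9.4 says antifungal prophylaxis should be considered in severe, prolonged neutropenia. That voriconazole is an antifungal is general knowledge; the protocol does not state it.

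**Working it through.** No statistical figure is involved. The check sets the texts side by side and works out the dose each one gives.

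**Inputs.** Standard dose 420 mg daily (section 7.1.1). Starting dose in Child-Pugh A 280 mg (section 7.4.1). Moderate-inhibitor dose 280 mg and strong-inhibitor dose 140 mg (section 7.7.2 and Appendix 10 agree on these). Class of voriconazole: moderate in section 7.7.2, strong in Appendix 10.

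**Formula.** Dose cut = (current dose − instructed dose) / current dose.

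| Patient needing voriconazole | Section 7.7.2 class (moderate) | Appendix 10 class (strong) |
|---|---|---|
| On 420 mg | 280 mg: (420 − 280)/420 = 33% cut | 140 mg: (420 − 140)/420 = 67% cut, or withhold |
| Child-Pugh A, on 280 mg | 280 mg: (280 − 280)/280 = 0% cut | combination not permitted by section 7.4.1 |

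For the patient on 420 mg the two instructed doses differ by a factor of 280/140 = 2.

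**Can the text settle the class?** No statement says which list prevails. Section 7.7.2 refers to Appendix 10 as its list of common inhibitors, and that is the list that contradicts its own example. Section 7.7.2 also points to an outside website for a comprehensive list, but does not say that it overrides either text. Seville oranges show the same split in class, but both texts say to avoid them, so no dose turns on it.

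**Withholding sentence in Appendix 10.** Its strong-inhibitor action prints two hold periods in succession: as long as the inhibitor is given, and at most 7 days. These agree for a course of up to 7 days and conflict for a longer one. The first phrase matches the Appendix 10 moderate row and the second matches the strong rule in section 7.7.2, which suggests editing residue, though that cannot be shown. Section 7.7.2 states the rule cleanly: 140 mg throughout, or a short hold.

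**Hepatic rule.** Section 7.4.1 is a specific bar for a subgroup; the last-resort text in section 7.7.2 and Appendix 10 is a general rule. Read together, the specific rule limits the general one. Only the 140 mg option is in tension with the bar; withholding ibrutinib is compatible with it.

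**The case against.** The best defence is that the protocol has several safeguards. Both classes are to be avoided. Section 4.2 excludes patients who need a strong inhibitor. Appendix 10 asks for pharmacy guidance on new medications and for toxicity monitoring with either class, and section 7.7.1 invites consultation if a site is unsure. One can also argue that Appendix 10 is the reference list and so prevails.

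These points lower the risk and support calling it minor. They do not remove the conflict. The disputed text applies exactly when avoidance has failed. The exclusion covers need at entry, not need that arises later. Pharmacy would be working from the same two lists, and a site that has read one clear instruction is not unsure. That Appendix 10 is the reference list is a good reason to resolve the mismatch in its favour, but the protocol does not state that precedence.

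A reader might go further and infer that section 7.4.1 is contradicted by the 140 mg option, so that the protocol both forbids and allows a strong inhibitor in hepatic impairment. The documents do not support this. The bar stands directly before the sentence that sets the Child-Pugh A dose, in the paragraph a site must use to dose such a patient, and section 7.1.1 refers to section 7.4.1 for dose modifications. Nor is its absence from the prohibited list in section 7.7.1 an error: ACE inhibitors and ARBs are listed there because they are barred for everyone on ibrutinib, whereas this bar concerns one subgroup. What remains is a useful cross-reference.

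It would also be too much to treat the doubled hold period as a safety hazard. Both texts offer 140 mg for a long course, and the longer hold means less drug exposure, not more.

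**Conclusion.** The voriconazole mismatch is a real inconsistency in operative dosing text. It gives a 33% or a 67% dose cut for a patient on 420 mg. For a Child-Pugh A patient on 280 mg it gives either no change or a combination that is not permitted. The percentages assume the patient is on the full starting dose for that group and that the 140 mg option, not the hold, is chosen under the strong class.

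The garbled withholding sentence is real but secondary, and the missing hepatic reminder is a matter of cross-reference only. The protocol does not say how many patients will need voriconazole or have chronic hepatic impairment. The hepatic group should be small, since Child-Pugh B and C are excluded at entry and section 4.1 sets limits on transaminases and bilirubin. Nothing here touches the MRD endpoint, the Bayesian activity rule or the toxicity stopping boundaries, so the point is minor safety wording, still worth correcting.

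**What to change.** 1. Delete voriconazole from the moderate examples in section 7.7.2 and name it among the strong ones, so that both texts give 140 mg or a short hold. This matches Appendix 10, the list to which sections 7.7 and 7.7.2 refer, and is the option with lower ibrutinib exposure. The small downside is a lower ibrutinib dose while the patient takes voriconazole.
2. Replace the strong-inhibitor action in Appendix 10 with the section 7.7.2 rule: 140 mg for as long as the inhibitor is given, or a temporary hold of at most 7 days.
3. Add to the strong-inhibitor text in both section 7.7.2 and Appendix 10 a short line such as: *not permitted in chronic hepatic impairment (see 7.4.1)*. This restates the existing rule where sites will be looking and does not change it.

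The cost is wording in a protocol amendment. No extra data, patients or procedures are needed.
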